12.3.2 Sensitivity Analyses

No sensitivity analyses will be performed for the other efficacy endpoints.

 Innovaderm Research	STATISTICAL ANALYSIS PLAN, Final Version 1.0
Protocol Number: ARQ-151-313	Sponsor: Arcutis Biotherapeutics, Inc.

12.3.3 Subgroup Analyses

The main analysis of the other efficacy endpoints of achievement of at least a 4-point reduction on the WI-NRS, EASI-50, and EASI-75 will be repeated for the subgroups mentioned in Section 6.6 (including subgroup analysis for achievement of at least a 4-point reduction on the WI-NRS among subjects < 12 years old at entry in parent study). Additional subgroup analyses for duration, cumulative time and percent of time endpoints are also described in Section 6.6. Subgroup analyses will only be conducted for results relative to the primary baseline unless otherwise indicated in this SAP.

Subgroup analyses will not be performed for any other efficacy endpoints.

13 SAFETY ANALYSES

Safety analyses will be conducted using the safety population. No p-values or confidence intervals will be provided for safety endpoints, with the exception of EAIRs (refer to Section 5.5) which will be accompanied by 95% CIs.

13.1 Adverse Events

AEs will be coded according to the latest available version of MedDRA (Version 25.0 or higher).

A treatment emergent adverse event (TEAE) is defined as an AE that started post application of study medication at the Day 1 visit of study ARQ-151-313 or was present at treatment initiation but worsened during treatment, through study completion. See [Appendix 2](#) for handling of completely or partially missing dates for AEs. In the case where it is not possible to define an AE as treatment emergent or not, the AE will be classified as treatment emergent.

An overall summary of TEAEs will be presented by treatment group as defined in Section 5, which will include the total number of events, and the number and percentage of subjects who experienced at least one TEAE, TEAE by the maximum severity, TEAE by relationship and TEAE by the strongest relationship, treatment-emergent SAE, treatment-emergent Non-SAE, TEAE leading to study treatment discontinuation, TEAE leading to study discontinuation, TEAE on an application site, and TEAE leading to death. In addition, similar summary as described above will be presented by age group (refer to Section 6.6) for rollovers from study ARQ-151-311/312.

The number and percentage of subjects who experience at least one TEAE will be summarized by SOC, PT, and treatment group as defined in Section 5. A subject experiencing the same TEAE multiple times within the same PT will be counted only once for that PT. Similarly, a subject experiencing the same TEAE multiple time within the same SOC will be counted only once for

 Innovaderm Research	STATISTICAL ANALYSIS PLAN, Final Version 1.0
Protocol Number: ARQ-151-313	Sponsor: Arcutis Biotherapeutics, Inc.

that SOC. TEAEs will be sorted alphabetically by SOC and within each SOC, the PT will be presented by descending frequency. In addition, similar summary as described above will be presented by age group (refer to Section 6.6) for rollovers from study ARQ-151-311/312.

The number and percentage of subjects who experience at least one TEAE will also be summarized by SOC, PT, strongest relationship with study treatment (related or not related) and treatment group. A treatment-related TEAE is defined as any TEAE that is assessed by the Investigator as likely, probably, or possibly related to study treatment. TEAE that is assessed as unrelated or unlikely will be defined as not treatment-related. If a subject experiences more than one TEAE within different relationship categories within the same SOC/PT, only the worst case (the strongest relationship) will be reported. TEAE with an unknown relationship will be considered as treatment-related.

The number and percentage of subjects who experience TEAE will also be summarized by SOC, PT, maximum severity (mild/moderate/severe/life threatening/death related to AE), and treatment group as defined in Section 5. If a subject experiences more than one TEAE within different severity categories within the same SOC/PT, only the worst case (the maximum severity) will be reported. TEAE with an unknown severity will be considered as severe.

The number and percentage of subjects who had treatment-emergent SAE will be summarized by SOC, PT, and treatment group as defined in Section 5. TEAEs leading to study drug discontinuation and TEAEs leading to study discontinuation will be summarized similarly.

Frequency and percentage of subjects who experience TEAE on an application site will be summarized by SOC, PT, and treatment group as defined in Section 5.

A plot of most frequent TEAE ($\geq 1\%$) will be provided by PT and treatment group as defined in Section 5 (overall TEAE and overall treatment-emergent SAE will be included in the same plot).

The EAIR and the corresponding 95% CI will be reported for all tables of TEAEs by SOC and PT described earlier in this section. The EAIR per 100-pt year, defined in Section 5.5, will be calculated in each arm and the 95% CI will be calculated by using a Poisson regression model with number of TEAEs as dependent variable and log of exposure time as offset. Additionally, the difference in EAIR between the 'Roflumilast cream 0.15%' and 'Vehicle / Roflumilast cream 0.15%' treatment groups (refer to Section 5) will be provided along with the associated two-sided 95% CI.

All the AEs will be listed. TEAEs with an outcome of death, treatment-emergent SAEs, TEAEs leading to study discontinuation, and TEAE leading to study treatment discontinuation will be listed. The TEAE related to application site will be flagged in the AE listing.

 Innovaderm Research ■■■	STATISTICAL ANALYSIS PLAN, Final Version 1.0
Protocol Number: ARQ-151-313	Sponsor: Arcutis Biotherapeutics, Inc.

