6. DATA ANALYSIS

Data will be handled and processed according to the Contract Research Organization's Standard Operating Procedures, which are written based on the principles of GCP.

Full details of the statistical analysis will be included in the Statistical Analysis Plan (SAP).

Data from this study may be analyzed prior to the final analysis for regulatory reporting purposes. Under Amendment 1, subjects 6-17 years of age that have completed the 4-week treatment period in ARQ-151-311 or ARQ-151-312 will be treated for 24 weeks with ARQ-151 cream 0.15% (Cohort-Week 24). The rest of the subjects will be treated for up to 52 weeks with ARQ-151. The analysis will be performed by cohorts and overall over time.

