2 STUDY OBJECTIVES AND ENDPOINTS

OBJECTIVES	ENDPOINTS
Safety	
To assess long-term safety in subjects with atopic dermatitis (AD) treated with Roflumilast cream 0.15%	Primary safety endpoints: 
 • Treatment-emergent Adverse Events (TEAEs) • Serious Adverse Events (SAEs)

Protocol Number: ARQ-151-313

Sponsor: Arcutis Biotherapeutics, Inc.

OBJECTIVES	ENDPOINTS

once daily (QD; subjects \geq6 years of age) or Roflumilast cream 0.05% QD (subjects 2 to 5 years of age) after completing one of three Phase 3 studies (ARQ-151-311 or ARQ-151-312 or ARQ-151-315).
	
Other safety endpoints:
 
 Changes and percent change in clinical laboratory results Changes and percent change in vital signs Local tolerability assessments Change from baseline of Patient Health Questionnaire depression scale (PHQ-8) and Modified PHQ-9 for Adolescents (PHQ-A) total score Change from baseline of Children's Depression Inventory 2nd Edition (CDI-2) total score Columbia-Suicide Severity Rating Scale (C-SSRS)

Efficacy
 
To evaluate the long-term efficacy in subjects with AD treated with roflumilast cream 0.15% QD (subjects \geq6 years of age) or roflumilast cream 0.05% QD (subjects 2 to 5 years of age) after completing one of three Phase 3 studies (ARQ-151-311 or ARQ-151-312 or ARQ-151-315).
	
Secondary efficacy endpoints:
 
 Validated Investigator Global Assessment-Atopic Dermatitis (vIGA-AD) score of clear (0) or almost clear (1) at each assessment vIGA-AD success (defined as vIGA-AD score of clear (0) or almost clear (1) plus at least a 2-grade improvement from baseline) at each assessment In subjects \geq 12 years old at the start of the parent study, change and percent change from baseline in Worst Itch - Numeric Rating Score (WI-NRS) over time ^a Change and percent change from baseline in Eczema Area and Severity Index (EASI) total score over time 
Other efficacy endpoints:
 
 Duration of the first twice weekly (BIW) dosing interval Cumulative time (days) on BIW dosing

Protocol Number: ARQ-151-313

Sponsor: Arcutis Biotherapeutics, Inc.

OBJECTIVES	ENDPOINTS

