- SCORAD Total Score = [Overall BSA affected by AD / 5] + [Intensity score * 7/ 2] + Subjective symptoms score (i.e., pruritus + sleep loss), ranging from 0 to 103. SCORAD total score will be set to missing if information for any of the three measures is missing.
- Change from baseline = Assessment value at post-baseline visit X – baseline value.
- Percent change from baseline = (Assessment value at post-baseline visit X – baseline value) × 100% / (baseline value)

Percent change from baseline will be missing in situation where baseline value equals to 0.

- Exposure-adjusted incidence rate (EAIR) = (number of subjects with an event / total within-arm exposure [days]) * 365.25 days/year * 100.
- BMI (kg/m²) = (weight in kg)/ [(height in cm/100)²]. For child and adolescent (2 to 17 years), after BMI is calculated, it is expressed as a percentile using data files and instructions provided by the CDC (https://www.cdc.gov/growthcharts/percentile_data_files.htm).

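### No TEAE table or exposure-adjusted rate is split by time on drug, so the planned AE outputs will not show whether a rate rises after Week 24

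*SAP*

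**What the plan says.** SAP Section 2 sets the objective: "To assess long-term safety in subjects with atopic dermatitis (AD) treated with Roflumilast cream 0.15"% once daily, or the 0.05% cream in children aged 2 to 5. TEAEs and SAEs are the primary endpoints.

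The AE outputs are in SAP 13.1:

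- The overall summary gives "the total number of events, and the number and percentage of subjects who experienced at least one TEAE", with breakdowns such as severity, relationship, seriousness, discontinuation and application site.
- The window is single. A TEAE starts after the Day 1 application in the extension "or was present at treatment initiation but worsened during treatment, through study completion".
- Tables are by parent-study arm. The only further subject breakdown is age: a "similar summary as described above will be presented by age group (refer to Section 6.6) for rollovers from study ARQ-151-311/312".
- On rates: "The EAIR and the corresponding 95% CI will be reported for all tables of TEAEs by SOC and PT described earlier in this section".

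SAP 5.5 defines the EAIR as "number of subjects with an event / total within-arm exposure [days]) * 365.25 days/year * 100". SAP 13.1 takes its interval from a Poisson model with "number of TEAEs as dependent variable and log of exposure time as offset". Neither contains a time period.

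Protocol Section 6 says: "The analysis will be performed by cohorts and overall over time". SAP 3.6 replaces that sentence with summaries overall and by parent-study arm, on the ground that the cohort analyses were not needed. SAP 6.6 keeps a cohort split only for efficacy endpoints measuring duration or time in a state.

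**The concern.** The parent studies last 4 weeks. What the extension can add on AEs is whether new events appear, or known ones become more frequent, over the following 24 or 52 weeks. A whole-period rate answers that only if the rate is constant. If it changes, the EAIR is an average weighted by wherever the person-time happens to lie, and a late rise looks the same as a steady intermediate rate.

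The other safety domains do have a time axis in the SAP: laboratory tests, vital signs and weight, local tolerability, depression scales, C-SSRS and physical examination are all summarised by visit. The primary endpoints are not.

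**Working it through.** The documents give no AE rate or detectable increase, so there is no planned figure to reproduce. I applied the SAP 5.5 formula to a rate that changes at Week 24.

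**Inputs**
- Cohort-Week 24: 275 + 275 = 550 subjects (approximate, protocol Summary of Changes), all from 311/312.
- 52-week subjects in 311/312: 400, an assumption.
- 315 roll-overs: 1500 - 550 - 400 = 550, an assumption. All are 52-week subjects.
- Dropout: none, an assumption, varied in step 5.
- Event rates: 2.0 per 100 PY to Week 24, then 4.0. Assumptions.

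**1. Person-years, 311/312**
- To Week 24: 950 x 168 / 365.25 = 437.
- After Week 24: 400 x 196 / 365.25 = 215.
- Total: 652, of which 67% is early.

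**2. Subjects with a first event** (0.460 and 0.537 years per interval)
- To Week 24: 950 x (1 - exp(-0.02 x 0.460)) = 8.7.
- After: 400 x exp(-0.02 x 0.460) x (1 - exp(-0.04 x 0.537)) = 8.4.

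**3. What SAP 13.1 would report**
- EAIR = 100 x (8.70 + 8.42) / 651.6 = 2.63.
- Approximate 95% CI on the log scale: factor exp(1.96 / sqrt(17.1)) = 1.61, giving 1.6 to 4.2. This contains both true rates.
- A constant rate of 2.65 gives the same EAIR, but with 11.5 and 5.6 events in the two intervals instead of 8.7 and 8.4. Only a split separates the two cases.

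**4. Would a cohort split be enough?** No. In the 400 52-week subjects, the first-event counts are 400 x (1 - exp(-0.02 x 0.460)) = 3.66 and 8.42, over 184 + 215 = 399 PY. Their EAIR is 3.03, still one average.

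**5. Dropout.** If 20% of each cohort leaves at Week 12, person-years are (760 x 168 + 190 x 84) / 365.25 = 393 and 320 x 196 / 365.25 = 172, with 7.8 and 6.7 events. The EAIR is 100 x (7.83 + 6.73) / 565 = 2.58. The conclusion is unchanged.

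**6. Exposure is not stopped at the first event.** At a constant 100 per 100 PY, the SAP formula gives 80 over 24 weeks and 63 over 52 weeks. At 2 per 100 PY it gives 1.99 and 1.98. For common categories the EAIR falls with follow-up even when the rate is flat, which can mask a rise.

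**7. What a split at Week 24 would show for a doubling.** SE of the log rate ratio = sqrt(1/e1 + 1/e2); chance that the 95% CI excludes 1 = Phi(ln 2 / SE - 1.96). Events are e1 and e2.

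| Early rate per 100 PY | 311/312: events | Chance | 311/312, Cohort-Week 52 only: events | Chance |
|---|---|---|---|---|
| 2 | 8.7, 8.4 | 30% | 3.7, 8.4 | 20% |
| 5 | 21.6, 20.4 | 61% | 9.1, 20.4 | 41% |
| 10 | 42.7, 38.9 | 88% | 18.0, 38.9 | 68% |

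**The case against.** Several points limit how far this goes.

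- **A reader might infer that AE risk is reported only as one average rate.** It is not. Counts and percentages are planned, and EAIRs are given per arm for each SOC and PT. All of these are still whole-period.
- **A reader might infer that the study cannot detect a late rise.** The documents do not support that. All AEs are listed (SAP 13.1), Study Day exists to show when events start and end (SAP 5.3), and exposure is listed (SAP 11). The gap is in the planned analysis. Listings alone give no rate, denominator or interval.
- **A reader might take the protocol sentence as a promise of AE rates by interval.** It is general and does not mention AEs, and SAP 3.6 declares the change. What stands is that the stated reason concerns cohorts and does not address time for AEs.
- **Early weighting is not universal.** The 315 roll-overs are all 52-week subjects, each contributing 168 days before Week 24 and 196 after if there is no dropout. Their average leans late. It still hides the change.
- **Much relevant safety is already by visit**, including weight change above 5%, depression scales and C-SSRS. This covers some of the concerns known from oral roflumilast, but it does not replace AE rates.
- **A split is confounded and imprecise.** Cohort-Week 24 is entirely aged 6-17 and leaves at Week 24, so the age mix in 311/312 changes at exactly that point. Some subjects move to BIW from Week 4. Rare events give wide intervals. These points stand and shape the fix.

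The planned EAIR difference between parent-study arms does not fill the gap: those arms differ by only about 4 weeks of prior roflumilast exposure.

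**Conclusion.** The point holds for the planned outputs. Nothing in SAP 13.1 relates AE frequency to time on drug, and the EAIR as defined cannot tell a doubling after Week 24 from a flat rate: about 2.6 per 100 PY in either case for the 311/312 roll-overs. The size rests on assumed numbers (400 52-week subjects, the event rates, no dropout). The absence of any time split does not.

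The omission makes no planned figure wrong, and the study is descriptive with no hypothesis tests. It is a gap in how the primary objective is answered, and cheap to close. The gain is real for common events and modest for rare ones.

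**What to change.** Add to SAP 13.1 the EAIR with 95% CI by onset interval:

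- **Intervals:** at least Weeks 0-24 and after Week 24. Use finer intervals only for any TEAE and other common categories.
- **Denominator:** person-time at risk within each interval, ending at the subject's first event of that type. State the numerator once: the SAP 5.5 formula counts subjects, while the SAP 13.1 model counts TEAEs.
- **Scope:** any TEAE, SAEs, TEAEs leading to discontinuation, SOCs and PTs. Apply no 1% cutoff, which could hide late-onset PTs.
- **Groups:** 311/312 and 315 roll-overs separately. Within 311/312, repeat the comparison in Cohort-Week 52 alone, so that the same cohort is seen in both intervals.
- **Interpretation note:** some subjects move to BIW from Week 4, and roflumilast-arm roll-overs enter with about 4 weeks of prior exposure.

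The cost is one extra table family, with no change to data collection or conduct. Intervals will be wide for rare events, above all after Week 24: for 3.7 and 8.4 events, the 95% limits of the rate ratio lie a factor of exp(1.96 x sqrt(1/3.66 + 1/8.42)) = 3.4 either side of the estimate. Fixing the intervals in advance avoids choosing them after the data are seen.

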5.7 Statistical Tests

No hypothesis tests are planned for this study; therefore p-values will not be provided. For estimation purposes, two-sided 95% confidence interval (CI) will be supplied for secondary efficacy endpoints and EAIRs.

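### The regression-based confidence interval for the EAIR has no finite estimate in an arm with zero events, and the SAP states no fallback, no method for the difference and no matching numerator

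*SAP*

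**What the plan says.** SAP 2 makes TEAEs and SAEs the primary safety endpoints. SAP 13 allows confidence intervals for safety only on EAIRs, and SAP 5.7 sets the level: "two-sided 95% confidence interval (CI) will be supplied for secondary efficacy endpoints and EAIRs".

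SAP 5.5 defines the rate as ("number of subjects with an event / total within-arm exposure [days]) * 365.25 days/year * 100". SAP 13.1 sets the scope: "The EAIR and the corresponding 95% CI will be reported for all tables of TEAEs by SOC and PT described earlier in this section". That takes in the relationship, maximum-severity, discontinuation, application-site and age-group tables. It also takes in the SAE table: "The number and percentage of subjects who had treatment-emergent SAE will be summarized by SOC, PT, and treatment group". The 1% cut-off in SAP 13.1 applies to a plot only, so rarer terms stay in the tables.

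The interval method, to be applied in each arm, is: "95% CI will be calculated by using a Poisson regression model with number of TEAEs as dependent variable and log of exposure time" as offset. SAP 13.1 then asks for "the difference in EAIR between the" two arms of the ARQ-151-311/312 rollovers, which "will be provided along with the associated two-sided 95% CI". No method is given for that interval.

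Under SAP 5 each rollover population is shown by parent-study treatment and pooled, with 311/312 kept apart from 315. SAP 5.5, 5.7, 6.2 and 13 contain no rule for an arm with zero events.

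**The concern.** A Poisson model with log exposure as offset works on the log-rate scale, where a rate of zero has no finite value. In a long-term safety study the informative statement about a rare or serious term is often how high its rate could be when none or one was seen. The stated method does not deliver that statement at zero, and at one to three events its usual limits sit too high.

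The SAP leaves the programmer to choose what to print in such a cell and how to form the interval for the difference, and both choices concern a primary endpoint. In addition, an interval built on event counts need not contain a rate built on subject counts.

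**Working it through.** The documents state no EAIR, event rate, arm size or interval width, so there is no planned figure to reproduce. Exposure T, arm size N and arm share w below are assumptions.

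**1. Zero events.** The log-likelihood for rate λ is −λT. It increases as λ falls to 0, so log λ has no finite maximum.
- Intercept-only Poisson fits to simulated arms with no events stopped with a boundary error.
- A joint two-arm fit with 4 and 0 events reported convergence, but gave the empty arm a log rate of −25.2 with standard error 15,917. Its Wald interval is in effect 0 to infinity.

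**2. What an exact interval gives.** With x subjects in T person-years, the limits are χ²(0.025; 2x)/(2T) and χ²(0.975; 2x+2)/(2T). At x = 0 the lower limit is 0 and the upper is −ln(0.025)/T = 3.689/T.

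| Assumed T (PY) | Exact upper limit at 0 events, per 100 PY |
|---|---|
| 100 | 3.69 |
| 300 | 1.23 |
| 600 | 0.61 |

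The 600 PY row is near the top of what is plausible. The protocol's Summary of Changes gives about 275 + 275 = 550 subjects for Cohort-Week 24, out of about 1500. With no dropout the total is 550 × 0.46 + 950 × 1.00 ≈ 1,200 PY over four parent-treatment groups.

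**3. One to three events, assumed 600 PY.** The Wald limits are (100x/T)·exp(±1.96/√x).

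| Events | Rate per 100 PY | Wald | Exact |
|---|---|---|---|
| 1 | 0.167 | 0.023 to 1.18 | 0.004 to 0.93 |
| 3 | 0.50 | 0.161 to 1.55 | 0.103 to 1.46 |

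Both Wald limits are shifted upward. At three events the upper limit is about 6% too high (1.55/1.46).

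**4. How often an arm is empty.** If n subjects in a row fall into two arms with shares w and 1−w and equal rates, the chance that one arm is empty is wⁿ + (1−w)ⁿ.

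| n | w = 1/2 | w = 2/3 |
|---|---|---|
| 1 | 100% | 100% |
| 2 | 50% | 56% |
| 3 | 25% | 33% |
| 5 | 6% | 14% |

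By arm size the chance of no events is (1−p)^N. At incidence p = 0.5% it is 37% for N = 200 and 5% for N = 600. At p = 1% it is 13% and 0.2%.

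**5. Numerator.** Suppose 10 subjects have 20 events in 200 PY. By SAP 5.5 the EAIR is 100 × 10/200 = 5.0. The regression on event counts estimates 100 × 20/200 = 10.0, with Wald limits 10.0 × exp(±1.96/√20) = 6.45 to 15.5. The interval excludes the rate it is meant to accompany.

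**The case against.** Several points on the other side stand.

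- **Reach.** A reader might infer that a sparse row loses its intervals altogether, or that many rows and most SAE terms will. The documents do not support this. Only the empty arm's cell is lost, together with any difference taken from the model. The non-empty arm keeps its interval. So does the pooled column in an unsplit table, because a listed term has at least one affected subject. Every treated subject in this study receives roflumilast, so the pooled column is an important summary. Frequency depends on event rates and arm sizes that are not given, and empty arms are unlikely in common SOC rows.
- **Type of interval.** SAP 13.1 names a model, not Wald limits. A profile-likelihood interval from the same model has a finite upper limit at zero, 1.92/T: 0.64 per 100 PY at an assumed 300 PY, against 1.23 for the exact limit. So the model can yield a limit at zero, but the SAP does not choose this one, and the two answers differ about twofold.
- **Direction.** At one to three events the Wald upper limit is too high, which errs towards caution.
- **The difference.** A reader might infer that a log-link model yields only a rate ratio and so can never supply a difference. That is too strong. Arm-specific rates and a delta-method interval can be formed when both arms have events, and the SAP does not say that the regression is the source. What stands is that no method is named, and that a model-based one breaks down when an arm is empty.
- **Consequence.** No tests are planned, counts and percentages are tabulated, and all AEs are listed, so no event goes unreported. SAP 5 places table layouts in a separate document, which might contain a display convention for such cells. A display convention would still not supply an upper limit.

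**Conclusion.** The point holds within limits. As written, the interval method fails for any arm with zero events, and the SAP has no fallback. This is certain for one of the two parent-treatment arms in each SOC/PT row with a single affected subject. It is possible in other sparse SAE, severity, relationship and age-group rows.

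What is lost in such a cell is an upper limit of 3.69/T, or 0.61 to 3.69 per 100 PY over an assumed 600 down to 100 PY. How many cells are affected cannot be computed from the documents. The failure at zero assumes the usual Wald limits; under profile likelihood the defect is an unspecified choice, not an impossible one.

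Two further gaps do not depend on that assumption. The interval for the EAIR difference has no stated method, and the regression outcome does not match the EAIR numerator. The numerator mismatch can matter at any count, wherever subjects have repeated events. Reporting of counts is unaffected and no hypothesis test is involved, so this is a correctable weakness in how the primary safety rates are estimated.

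**What to change.** In SAP 13.1:

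1. Replace the Poisson regression with exact Poisson (chi-square) limits for each arm. Use the number of subjects with an event as the count and the same exposure denominator as the EAIR in SAP 5.5. At zero events this gives 0 to 3.689/T with no special rule, and it removes the numerator mismatch.
2. Name an interval for the EAIR difference that is defined when an arm has zero events, for example a Miettinen-Nurminen score interval for rate differences, or MOVER built from the exact limits.

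The cost is a change of SAP wording and simpler programming than the regression, with no new data. Exact limits are slightly conservative.

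### The EAIR is defined on subjects with an event, but SAP 13.1 takes its 95% CI from a plain Poisson model of TEAE counts, so intervals for common AE rows are miscalibrated

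*SAP*

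**What the plan says.** TEAEs and SAEs are the primary endpoints (SAP 2). SAP 5.5 gives the EAIR as "number of subjects with an event / total within-arm exposure [days]) * 365.25 days/year * 100", and SAP 5.6 restates it as subjects with events per 100 subject-years. The SOC/PT tables in SAP 13.1 count a subject once per term and once per class.

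The interval is described differently. SAP 13.1 says it is "calculated by using a Poisson regression model with number of TEAEs as dependent variable and log of exposure time as offset". Nothing there or in SAP 5.5 to 5.7 mentions a scale parameter, a negative-binomial model or a robust variance. For the EAIR difference between the prior-roflumilast and prior-vehicle groups, SAP 13.1 says only that it "will be provided along with the associated two-sided 95% CI", with no method.

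SAP 5.7 states: "No hypothesis tests are planned for this study; therefore p-values will not be provided". SAP 13 adds: "No p-values or confidence intervals will be provided for safety endpoints, with the exception of EAIRs".

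**The concern.** The point estimate counts subjects and the interval counts TEAEs. In a rare row the two counts are nearly equal. In a common row they are not, because a subject followed for 24 or 52 weeks can have several TEAEs in one class.

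The variance is a second problem. A Poisson model sets the variance equal to the mean. That is too small for event counts if some subjects are more prone to AEs than others, and too large for a 0/1 outcome, whose variance is p(1-p) and not p.

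What is at stake is the only stated precision on the primary safety endpoint, and the only between-group interval in the SAP.

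**Working it through.** The documents give no AE rate, dispersion or group size, so there is no planned figure to reproduce. **Assumed inputs:** 500 subjects per group; 45% followed 24 weeks (T = 24/52 = 0.4615 years) and 55% followed 52 weeks (T = 1); event rate λ per year; between-subject gamma frailty variance θ. The 24- and 52-week durations are from SAP 3.1.

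Mean exposure is 0.45 × 0.4615 + 0.55 × 1 = 0.7577 years per subject.

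**Reading A: all events are counted (λ = 1.0, θ = 0).**
- Probability of at least one event, 1 - exp(-λT): 0.3697 at 24 weeks and 0.6321 at 52 weeks. Mean 0.45 × 0.3697 + 0.55 × 0.6321 = 0.5140.
- EAIR as defined: 0.5140/0.7577 = 67.8 per 100 subject-years. Event rate: 100.
- Expected events: 500 × 0.7577 = 378.8. CI: 100 × exp(±1.96/√378.8) = 90.4 to 110.6.

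The reported EAIR lies well outside its own interval, even with independent events and a correct variance. A robust variance alone does not help, because it changes the width and not the centre: coverage of the defined EAIR stays at 0%.

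If subjects also differ in AE propensity, variance/mean = 1 + θλE[T²]/E[T]. Here E[T²] = 0.45 × 0.2130 + 0.55 = 0.6459, and 0.6459/0.7577 = 0.852. At λ = 1 the ratio is 1.43, 1.85 and 2.70 for θ = 0.5, 1 and 2. Coverage of the event rate is 2Φ(1.96/√ratio) - 1 = 90%, 85% and 77%. At θ = 0 it is 95%, so repeated events by themselves do no harm.

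**Reading B: each subject is counted once.** Let r be the EAIR per year and p(T) = 1 - (1 + θλT)^(-1/θ), or 1 - exp(-λT) at θ = 0. The true variance per subject is V = E[p(1-p)] + E[(p - rT)²]; the Poisson model uses E[p]. With φ = V/E[p], the standard error is 1/√φ times the correct one, and coverage is 2Φ(1.96/√φ) - 1. At λ = 1 and θ = 0: V = 0.2354, φ = 0.2354/0.5140 = 0.458, SE ratio 1.48, coverage 99.6%.

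| λ per year | θ | EAIR per 100 | φ | SE ratio | Coverage |
|---|---|---|---|---|---|
| 1.0 | 0 | 67.8 | 0.458 | 1.48 | 99.6% |
| 1.0 | 2 | 47.2 | 0.636 | 1.25 | 98.6% |
| 0.3 | 0 | 26.5 | 0.779 | 1.13 | 97.4% |
| 0.3 | 2 | 22.0 | 0.821 | 1.10 | 97.0% |
| 0.05 | 0 | 4.9 | 0.958 | 1.02 | 95.5% |

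Simulation on these inputs agrees: 98.5-99.7% at 1.0 per year, about 97-98% at 0.3, and 94-96% once a subject-level robust variance is used.

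**Second set of assumptions** (600 and 300 subjects, 40% followed 24 weeks and 60% followed 52, 20% dropout, 4,000 simulated trials per setting). At 0.8 events per year the event-count interval contained its own EAIR in 0% of trials. On the 0/1 outcome, plain Poisson covered 97.0-99.2% at 0.3 to 0.8 per year; robust variance covered 94.8-95.8% across all rates.

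**Group difference** (second set, assuming the same model is used). With equal rates both differences are zero, so only the width matters. With event rates of 0.8 and 1.1 per year and frailty variance 3, the event-rate difference is 30 per 100, but the EAIR difference is 44.4 - 37.8 = 6.6. The event-count interval covered the EAIR difference in 33% of trials.

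**The case against.** A reader might infer something stronger: that repeated TEAEs are wrongly treated as independent, so the EAIR intervals are too narrow and the difference interval excludes zero too often. The documents do not support that.
- Repeats are not in the EAIR numerator, since SAP 5.5, 5.6 and the table counting rule all count subjects.
- Under-coverage of an event rate needs between-subject heterogeneity, which the documents do not quantify.
- The method for the difference CI is not stated.
- On the SAP's own definition, plain Poisson errs the other way and is conservative.

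It can also be said that the count named in SAP 13.1 is loose wording for subjects with a TEAE, that plain variance is inferred from silence, and that little hangs on the result: no tests are planned, the CIs are for estimation, and the protocol's primary analysis tabulates TEAEs and SAEs.

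Most of this stands, and it limits the point. It does not remove it. The sentence followed literally gives an interval for a different quantity. Read charitably, it still gives an interval for common rows that is too wide, with or without heterogeneity.

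**Conclusion.** The concern holds as a mismatch between the EAIR's numerator and the outcome of its CI model, together with a variance that suits neither reading in common rows. Counting events puts the interval around the wrong quantity, and makes it too narrow for that quantity if subjects differ in AE propensity. Counting subjects once makes it too wide: a standard error 1.25 to 1.5 times too large at 1.0 events per year, and 97-98% coverage at 0.3 per year. Rows near 0.05 per year are essentially unaffected.

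All sizes rest on assumed rates, group sizes, follow-up mix and frailty. The too-wide result also assumes that exposure runs to the end of treatment, as the total exposure in SAP 5.5 implies. If exposure stopped at the first event and the hazard were constant, the Poisson variance would be about right.

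This is a correction to error bars on the primary safety endpoint. It changes no decision rule.

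**What to change.** In SAP 13.1:
- Use the 0/1 subject-with-event indicator as the dependent variable, with one record per subject per row (subjects without the event included) and the log-exposure offset.
- Compute each group's CI from a subject-level robust (sandwich) variance, for example PROC GENMOD with a REPEATED statement by subject. With D subjects with the event, outcome b and rate r, the variance of log r is Σ(b - rT)²/D².
- Compute the CI for the EAIR difference by the delta method from the same variances v: (r1 - r0) ± 1.96 × √(r1²v1 + r0²v0).
- Use an exact Poisson interval for very sparse rows, where the sandwich estimate is unstable.
- If an event rate is also wanted, report it separately, labelled as events per 100 subject-years, with robust or negative-binomial variance.

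The cost is a few sentences in the SAP and one more program statement, with no new data and no protocol amendment. Any event-rate CIs would become wider.
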